## **General Objective**

To characterize the immunogenicity induced by COVID-19 vaccines in Mexican population: mRNA expression for IgG anti-spike.

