## **Methodology**

Type of study, general design and population

A quasi-experimental, longitudinal, retrospective, comparative, quasi-experimental study will be carried out in a Mexican population older than 18 years with a complete vaccination schedule against COVID-19, to determine the immunogenicity induced by the vaccines.

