### **Four study groups will be formed.**

- Group 1: 20 persons who have received the Oxford/AstraZeneca vaccine (ChAdOx1 nCoV-19).
- Group 2: 20 persons who received the Gamaleya National Center vaccine (Sputnik V).
- Group 3: 20 people who have received the Pfizer/BioNTech vaccine (BNT162b2)
- Group 4: 20 persons who have received Sinovac vaccine (CoronaVac)

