### **Inclusion criteria:**

- 1.- Persons of Mexican origin.
- 2.- Over 18 years of age.
- 3.- With complete vaccination schedule against COVID-19.
- 4.- Allowing peripheral blood samples to be taken.
- 5.- To sign an informed consent form.
- 6.-Who agree to participate in the protocol.

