#### **Procedure:**

(a) Participants were selected by clinical history to assess current health status, obtain demographic data, as well as personal pathological history of importance for the study (chronic degenerative diseases, history of COVID-19 disease).

b) Peripheral venous blood samples (3 ml per occasion) will be taken from all participants. They will be carried out on days 30,60 and 120 after completion of the COVID-19 vaccination schedule.

c) Sample processing:

tRNA extraction from all samples.

cDNA synthesis

Real time PCR performance.

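### The plan aims at immunogenicity induced by the vaccines, but with only post-vaccination samples and no unvaccinated group it can describe expression after vaccination, not what a vaccine induced

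*Combined protocol and SAP*

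**What the plan says.** The General Objective is "To characterize the immunogenicity induced by COVID-19 vaccines in Mexican population: mRNA expression for IgG anti-spike". The Methodology section states the same target: the study is done "to determine the immunogenicity induced by the vaccines".

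On sampling, item (b) of the Procedure says of the blood draws: "They will be carried out on days 30,60 and 120 after completion of the COVID-19 vaccination schedule". No draw before vaccination is planned.

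On groups, "Four study groups will be formed", each defined by a vaccine already received; for example, "Group 1: 20 persons who have received the Oxford/AstraZeneca vaccine (ChAdOx1 nCoV-19". Inclusion requires "With complete vaccination schedule against COVID-19", and an incomplete schedule is an exclusion, so nobody in the study can serve as an unvaccinated reference.

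On earlier infection, item (a) of the Procedure collects "personal pathological history of importance for the study (chronic degenerative diseases, history of COVID-19 disease". The Exclusion criteria do not mention prior COVID-19, and the Elimination criteria cover only COVID-19 that develops during the study.

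The Statistical analysis section lists descriptive summaries, two-group tests, Kruskal-Wallis and Friedman. It has no baseline term and no stratification, adjustment or restriction by COVID-19 history.

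**The concern.** There are two distinct problems.

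The first is identification. What a vaccine induces is the difference between expression after vaccination and expression without it. The plan observes only the former. A day-30 value combines vaccine response, any response to earlier infection and the person's background level, and nothing in the design separates them. The marker does not help: the protocol describes spike as a structural protein of the virus itself, so an anti-spike response may come from infection as well as from a vaccine. The Hypothesis section goes further and judges whether the response is enough to prevent renewed infection, so readers are likely to take the results as statements about vaccine effect.

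The second is confounding of the comparison between vaccines. The study does not assign vaccines. If the groups differ in the share of people with earlier infection, and if such people have higher expression, the unadjusted tests may attribute the difference to the vaccine.

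**Working it through.** The documents give no sample-size calculation, SD or effect size, so there is no figure of the plan's own to reproduce. The only design figures are 4 groups × 20 = 80 people and three draws each, 240 samples.

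**Identification.** Write expected expression as

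μ + τ(vaccine) + γ × (prior infection) + δ(day),

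where μ is the unvaccinated, never-infected level at day 30 and τ is the induced part. The columns are 1 intercept + 4 vaccine indicators + 1 prior-infection indicator + 2 day indicators = 8. Taking every combination the plan can observe, 4 vaccines × 2 histories × 3 days = 24 rows, the matrix has rank 7. The cause is exact: everyone has one of the four vaccines, so the four indicators sum to the intercept.

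- Estimable: μ + τ for each vaccine, differences in τ between vaccines, the changes to days 60 and 120 and, if history were modelled, γ.
- Not estimable: μ and τ separately. No increase in sample size alters this.
- Adding unvaccinated people sampled on the same days (2 × 3 = 6 more rows, 30 in all) brings the rank to 8. The contrast would still be non-randomised.

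**Confounding by prior infection.** This is an illustration of the second problem, not a measure of the first. All inputs are assumptions: two equally effective vaccines, prior-infection shares of 20% and 50%, expression k-fold higher after infection, and an SD of 1.5 log2 units within infection strata.

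Gap in mean log2 expression = (0.50 − 0.20) × log2(k).

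The mix of infected and uninfected people widens the SD within a vaccine group. Averaged over the two groups, total variance = 1.5² + log2(k)² × (0.2 × 0.8 + 0.5 × 0.5)/2 = 2.25 + 0.205 × log2(k)².

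| k | Gap (log2) | Fold | Total SD | Gap in SD |
|---|---|---|---|---|
| 2 | 0.30 | 1.23 | √2.455 = 1.57 | 0.19 |
| 4 | 0.60 | 1.52 | √3.070 = 1.75 | 0.34 |
| 8 | 0.90 | 1.87 | √4.095 = 2.02 | 0.44 |

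**Against what the design can detect.** With 20 per group, 80% power and two-sided 0.05 (both assumed; the plan gives only the 0.05 level, not its sidedness), a two-sample t-test detects 0.91 SD. The normal approximation gives (1.960 + 0.842) × √(2/20) = 0.89 SD. The whole illustrated range lies below this.

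**Effect on false positives.** Simulating the same set-up with 20 per group and the planned Mann-Whitney test at 0.05, the two equally effective vaccines are declared different in about 8 to 9%, 18 to 19% and 28% of studies for k = 2, 4 and 8. With equal shares the rate stays at about 5%.

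**How large an imbalance is plausible.** By chance alone, the difference in share between two groups of 20 has SD √(2p(1 − p)/20): 0.126 at p = 0.2 and 0.158 at p = 0.5, so 13 to 16 percentage points. A 30-point gap is about 1.9 to 2.4 of these, and so would normally need a systematic difference between the groups.

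**Cost of restricting to people without prior infection.** At an assumed share of 20% to 50%, 20 × 0.8 = 16 down to 20 × 0.5 = 10 remain per group. By the normal approximation the detectable difference rises from 0.89 to 0.99 (n = 16) or 1.25 SD (n = 10).

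**The case against.** The strongest reply is that the objective's verb is only to characterise, and that every planned test compares groups or time points, which the design supports. No test or success criterion concerns induction, so the fault rests on a causal adjective in two sentences. This stands in part: the analyses are usable as they are, and the study keeps its descriptive value. It does not remove the point, because the objective, the design statement and the hypothesis are what a reader will set the results against.

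Three stronger readings are tempting and should not be drawn.

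- *That people with prior COVID-19 are in the study.* The documents do not say so. They are not excluded, and history is collected when participants are selected; whether it influenced selection is not stated.
- *That the comparison between vaccines will be biased.* Bias needs both an imbalance in prior infection and higher expression after infection. The documents give a figure for neither. A group with more previously infected people may look more immunogenic; that is as far as the text goes.
- *That the illustrated gap measures the missing baseline.* It sizes confounding between vaccines. Perfect balance on prior infection would leave the induced part just as unidentifiable.

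The label retrospective is also defensible if it refers to vaccination that has already happened. The documents leave this open; the difficulty is only that the same study takes its blood samples forward in time.

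**Conclusion.** The point holds as a mismatch between claim and design. That the induced response cannot be identified follows from the sampling days and the group definitions, and needs no numerical assumption. The plan supports description of post-vaccination anti-spike IgG mRNA expression, its course from day 30, and non-randomised differences between vaccines.

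The exposure to confounding by prior infection is real but of unknown size. The range of about 0.2 to 0.44 SD depends wholly on the assumed shares, fold-differences and within-stratum SD. It is too small for the design to detect reliably, but large enough under those assumptions to push the error rate of a pairwise vaccine comparison above 5%. The plan should be changed because the correction is cheap and the stated conclusion would otherwise be unsupported; it is not a reason to regard the study as without value.

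**What to change.** 1. Reword the General Objective and the Methodology statement to: describe anti-spike IgG mRNA expression after vaccination, its change from day 30 to days 60 and 120, and differences between vaccine groups. State that no claim of a vaccine-induced response is made.
2. Align the Hypothesis section with this, since its present wording about sufficient immunogenicity would conflict with the reworded objective.
3. State that the study does not assign vaccines, and reconcile the terms retrospective and quasi-experimental with draws that are still to be taken.
4. In the Statistical analysis section, prespecify that the vaccine comparison is shown by recorded history of COVID-19, with the result in people without such history beside the overall result.

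This needs no new visits, blood or participants. The costs are a narrower claim and the loss of numbers shown above for the no-history comparison. The split reduces the bias without removing it: the protocol's own account of COVID-19 says infection can be asymptomatic, so the no-history stratum may contain people who were infected unknowingly. It also does not restore the missing reference level.

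If the sponsor wishes to keep a claim about induction, a concurrent unvaccinated group sampled on matching days would be needed. At 20 people it would detect about 0.89 SD against one vaccine group (normal approximation, same assumed power and alpha) and would remain a non-randomised contrast. A pre-vaccination sample cannot be obtained from people who are already vaccinated when they enter.

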According to the information provided by WHO, it is vital to continue research to answer a number of questions about the vaccines currently in use, which have been licensed for emergency use to combat the COVID-19 pandemic. One of the most worrisome questions concerns the duration of the immunity conferred by these vaccines and, moreover, whether they will protect the population from the new SARS-CoV-2 strains that continue to appear.

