## **Vaccines and COVID-19**

To date, there is no specific treatment for COVID-19. For this reason, efforts have focused on preventing the spread of the disease through mitigation measures and on seeking herd immunity, also known as flock immunity, through vaccination. Research conducted after the SARS-CoV epidemic in 2003 has laid the groundwork for the development of vaccines against COVID-19, due to the genetic similarity shared by both CoVs.

Historically, the implementation of vaccination programs, especially during childhood, has been the key to controlling and/or eradicating countless infectious and contagious diseases. Vaccines prepare the immune system to create immunoglobulins that can later recognize the pathogen in question and attack it, thus breaking the chain of disease transmission.

As of June 3, 2021, WHO has assessed that the following COVID-19 vaccines meet the criteria of safety and efficacy for population use.

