## **Hypothesis**

Gene expression for IgG anti-spike in subjects with a complete vaccination schedule against COVID-19 does not develop the necessary immunogenicity in the Mexican population to prevent re-contagion.

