## **Specific objectives**

1. Determine the mechanisms of virus transmission on the cell.
2. To identify the study population.
3. To identify the anti-spike IgG genes in vaccinated population.

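### The only measurement is anti-spike IgG transcript in blood, but the plan labels it immunogenicity and hypothesises that it is too low to prevent re-infection; nothing collected can support that conclusion

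*Combined protocol and SAP*

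**What the plan says.** - **General Objective:** "To characterize the immunogenicity induced by COVID-19 vaccines in Mexican population: mRNA expression for IgG anti-spike". The design statement under Methodology likewise gives vaccine-induced immunogenicity as what the study will determine.
- **Hypothesis:** gene expression for anti-spike IgG in fully vaccinated people "does not develop the necessary immunogenicity in the Mexican population to prevent re-contagion".
- **Specific objectives:** the only laboratory objective is "To identify the anti-spike IgG genes in vaccinated population".
- **Procedure:** "Peripheral venous blood samples (3 ml per occasion) will be taken from all participants", and "They will be carried out on days 30,60 and 120 after completion of the COVID-19 vaccination schedule". Processing starts with "tRNA extraction from all samples", followed by cDNA synthesis and real-time PCR. The Schedule lists the same steps.
- **Elimination criteria:** anyone who contracts COVID-19 while enrolled is removed.
- **Statistical analysis:** Kruskal-Wallis for more than two groups, Friedman for related samples, and the usual two-sample and paired tests, at P below 0.05. It does not say how a change or difference in transcript is to be interpreted.
- **Background:** "Vaccines prepare the immune system to create immunoglobulins that can later recognize the pathogen in question and attack it" (Vaccines and COVID-19), and "One of the most worrisome questions concerns the duration of the immunity conferred by these vaccines" (Introduction).

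**The concern.** The plan moves from a transcript measurement to a statement about immunity without a step in between. Its own background says that vaccines act through immunoglobulins, which are protein, yet no protein is measured. The hypothesis then goes further, from immunogenicity to the prevention of re-infection.

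What is at stake is the published conclusion. The design is longitudinal and comparative, so its natural results are a change across days 30, 60 and 120 and a difference between four named vaccines. Under the present objective and hypothesis, either could be reported as waning or inadequate immunity when no antibody or infection evidence has been collected. This would hold even if the PCR were perfectly specific for anti-spike IgG, as the objective intends.

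**Working it through.** The plan states no effect size, standard deviation or sample-size calculation, so there is no figure to reproduce. The check is a count, followed by a comparison of each possible conclusion with what is collected.

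**Count of measurements**

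- Participants: 4 groups × 20 = 80.
- Planned blood samples: 80 × 3 visits = 240, if every group is filled and every draw is made.
- Samples assigned to RNA extraction, cDNA synthesis and PCR: 240.
- Samples assigned to an antibody titre, ELISA, neutralisation test or other protein measurement: 0. Immunoglobulins and neutralizing antibodies appear only in the background sections.

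**Conclusion against evidence**

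| Conclusion | What it would need | What the plan collects |
|---|---|---|
| Transcript differs between vaccines or visits | PCR result by group and visit | Yes |
| Antibody level | An antibody assay, or evidence that transcript tracks antibody | Neither |
| Persistence of antibody | Antibody at repeated visits, or evidence that the two move together over time | Neither |
| Immunogenicity below what is necessary | A threshold for the measure used | No threshold |
| Failure to prevent re-infection | Infection outcomes, or a validated link from transcript to infection | Neither; those who develop COVID-19 are eliminated |

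Only the first row is supported.

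**Can the listed tests reach the hypothesis?** As described in the Statistical analysis, each test compares groups, visits or categories with one another. None compares the measurement with a fixed level. A significant Kruskal-Wallis result would say that the vaccine groups differ in transcript, and a significant Friedman result that transcript changes over time. Neither result, nor its absence, says whether expression is sufficient. The hypothesis is therefore left without a test as well as without a suitable measurement.

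**The case against.** **The measure is disclosed.** The objective names mRNA expression after its colon, so a reader can see what is read out. This stands, and it narrows the point to the label in the objective and design statement and to the claim in the hypothesis. It does not rescue that claim.

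**The plan does not say a decline will be read as lost immunity.** This also stands. There is no interpretation rule, so the most that can be said is that results could be misread. The hypothesis makes such a reading easy but does not prescribe it.

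**Duration of immunity is background.** It is raised in the Introduction and appears in neither the hypothesis nor the objectives. Three visits imply a comparison over time, not a claim about how long immunity lasts. Persistence therefore belongs here only as something the data could not show.

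**The divergence of transcript and antibody is general biology.** The documents do not describe it. Nor do they name a cell fraction: the sample is peripheral venous blood. The point does not need a specific mechanism, because the plan gives no justification for treating transcript as a stand-in for antibody.

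**Stronger readings that the documents do not support.** A reader might infer that transcript falls faster than antibody, so that the mismatch favours the stated hypothesis. That rests on kinetics the documents do not give. Take an assumed antibody half-life of 21 days, with none sustained after day 30. An assumed transcript half-life of 10 days leaves 0.5^(90/10) = 0.2% of the day-30 transcript at day 120, against 0.5^(90/21) = 5% of the antibody. An assumed transcript half-life of 30 days leaves 0.5^(90/30) = 12.5% against the same 5%, and the direction reverses. A reader might also infer that vaccines will be ranked by immunogenicity; the plan specifies a test of difference between groups and no ranking.

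**Conclusion.** The concern holds as a mismatch between what is measured and what is to be concluded. All of the up to 240 planned samples yield transcript and none yields antibody. There is no threshold for the necessary immunogenicity, and those who become infected are eliminated. Conclusions about antibody level, its persistence or protection would be unsupported even with perfect execution.

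No numerical bias is claimed, and the direction of any misreading is not determined by the documents. The verdict assumes that the laboratory steps in the Procedure, which the Schedule repeats, are complete, and it takes the PCR target to be anti-spike IgG as stated. What the data can support is a comparison of transcript expression between vaccine groups and across visits.

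**What to change.** 1. **General Objective and the design statement under Methodology:** name the outcome as anti-spike IgG transcript expression in peripheral blood. Keep the anti-spike target, and change both places so that they agree.
2. **Hypothesis:** replace the claim of insufficient immunogenicity with one the data can test, for example that anti-spike IgG transcript expression differs between the vaccine groups or across days 30, 60 and 120. The Kruskal-Wallis and Friedman tests already listed can address these comparisons.
3. **Statistical analysis:** add that group differences and changes over time will be reported as transcript findings only, and not as antibody level, duration of immunity or insufficient protection.

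This needs no new participant, sample or assay. The cost is a narrower claim and a new hypothesis statement, which is a change of substance and should be recorded as such. If the sponsor wants a conclusion about antibody, anti-spike IgG would have to be measured as well. That is a larger change, and the documents do not say whether material for it is kept. A conclusion about protection would still need a threshold or infection outcomes.

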## **Specific objectives**

1. Determine the mechanisms of virus transmission on the cell.
2. To identify the study population.
3. To identify the anti-spike IgG genes in vaccinated population.

## **Methodology**

Type of study, general design and population

A quasi-experimental, longitudinal, retrospective, comparative, quasi-experimental study will be carried out in a Mexican population older than 18 years with a complete vaccination schedule against COVID-19, to determine the immunogenicity induced by the vaccines.

### **Four study groups will be formed.**

- Group 1: 20 persons who have received the Oxford/AstraZeneca vaccine (ChAdOx1 nCoV-19).
- Group 2: 20 persons who received the Gamaleya National Center vaccine (Sputnik V).
- Group 3: 20 people who have received the Pfizer/BioNTech vaccine (BNT162b2)
- Group 4: 20 persons who have received Sinovac vaccine (CoronaVac)

### **Inclusion criteria:**

- 1.- Persons of Mexican origin.
- 2.- Over 18 years of age.
- 3.- With complete vaccination schedule against COVID-19.
- 4.- Allowing peripheral blood samples to be taken.
- 5.- To sign an informed consent form.
- 6.-Who agree to participate in the protocol.

### **Exclusion criteria:**

- 1.- Persons with incomplete vaccination schedule against COVID-19.

Persons who have 30 +/- 5 days after having completed the COVID-19 vaccination schedule.

- 3.- People under treatment with any immunosuppressive drug.
- 4.- Persons who refuse to sign the informed consent.

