### **Statistical analysis**

Descriptive phase: The results were presented in tables for continuous variables with normal distribution in measurements  $\pm$  standard deviation and for free distribution in medians and percentiles. While the categorical variables were presented in percentages and total figures.

Bivariate phase: To look for differences in the quantitative variables according to the Kolmogorov-Smirnov normality test, the student t test or the Mann-Whitney U test were used or for the related ordinal variables the Wilcoxon test. The dichotomous or ordinal related qualitative variables were analyzed with the McNemar test, for the dichotomous or ordinal variables not related they were analyzed with the chi square test or Fisher's exact test.

Multivariate phase: To compare and find the differences in more than two groups in the quantitative variables with free distribution the Kruskall-Wallis test; for the related samples with free distribution the Friedman test was used. All calculations were performed using the current version of the SPSS statistical package for Windows and the Jamovi program version 4.1 of R. Statistical significance was considered to be a P value  $<0.05$  and a confidence interval of 95%.

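### The second exclusion criterion bars people 30 +/- 5 days past vaccination, the very window in which every participant must give the day-30 sample

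*Combined protocol and SAP*

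**What the plan says.** All of the text is in the combined protocol and SAP.

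- **Exclusion criteria**, the line between items 1 and 3: "Persons who have 30 +/- 5 days after having completed the COVID-19 vaccination schedule".
- **Exclusion criteria**, item 1: "Persons with incomplete vaccination schedule against COVID-19". This concerns whether the schedule is complete and sets no time limit.
- **Inclusion criteria**, item 3: "With complete vaccination schedule against COVID-19". Again there is no limit on time since the last dose.
- **Procedure (b)**: "Peripheral venous blood samples (3 ml per occasion) will be taken from all participants", and on timing, "They will be carried out on days 30,60 and 120 after completion of the COVID-19 vaccination schedule".
- **Elimination criteria**: these cover people who develop COVID-19 during the study and people who withdraw before their samples are complete. They do not cover people who arrive too late for day 30.

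No section says at what point after vaccination eligibility is judged, and none explains or reverses the exclusion line.

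**The concern.** The exclusion window and the sampling days share one time origin, completion of the vaccination schedule. An exclusion centred on the first sampling day bars the people who are ready to give that sample. People who have already missed it face no exclusion.

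The day-30 sample opens each participant's series and is the natural reference for change to day 60 or day 120. If the rule is applied as written, whether day 30 is missing depends on when the person was enrolled, and enrolment timing could differ between the four vaccine groups. The Statistical analysis section names the Friedman test for related samples. That test needs complete blocks, so a participant without day 30 drops out of a three-visit comparison. With 20 people per group there is little room for such losses. A reader would also be unable to tell which population had been studied.

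**Working it through.** The plan gives no figure of its own to reproduce here. The check compares an interval with the sampling days.

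**Inputs**

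- Exclusion window: 30 +/- 5 days after completing the schedule (Exclusion criteria).
- Sampling days: 30, 60 and 120 after completing the schedule, for all participants (Procedure (b)).
- Groups: 4 vaccine groups of 20 people (list of study groups).

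**Step 1. The excluded window.** 30 - 5 = 25 and 30 + 5 = 35, so days 25 to 35 are excluded. Day 30 is the midpoint. Days 60 and 120 lie outside.

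**Step 2. Who is excluded and what they could give**, by day of eligibility assessment:

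| Day assessed | Excluded by this line? | Scheduled samples still possible |
|---|---|---|
| 0 to 24 | No | 3 of 3 |
| 25 to 30 | Yes | 3 of 3 |
| 31 to 35 | Yes | 3 of 3 if a 5-day tolerance is allowed, otherwise 2 of 3 |
| 36 to 60 | No | at most 2 of 3 |
| 61 to 120 | No | at most 1 of 3 |
| After 120 | No | 0 of 3 |

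Procedure (b) states no visit tolerance, so the 31 to 35 row depends on an assumption. The table shows that the line turns away people who could give a full series and does not turn away anyone after day 35, none of whom can.

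**Step 3. Samples involved.**

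- Planned samples: 4 x 20 x 3 = 240.
- Day-30 samples: 4 x 20 = 80, and 80 / 240 = 33%.
- If eligibility is judged at the first draw, 80 of 80 day-30 samples come from people who meet the exclusion.
- If everyone is assessed on days 0 to 24, 0 of 80 do.

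The number affected therefore runs from 0 to 80, depending on a timing that the plan does not give. The 33% is the share of samples belonging to this visit. It is not an estimate of loss.

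**The case against.** The best defence is that the two rules can coexist. The Procedure puts selection by clinical history at step (a), before blood is drawn at step (b). If eligibility is judged once, at selection, and everyone is selected before day 25, nobody meets the exclusion and all three samples can be taken. This is logically possible, and under it no sample is affected. But the plan does not require or describe enrolment before day 25. It calls the study retrospective and defines the groups as people who have already been vaccinated. This reading also gives no reason to bar exactly the first visit window.

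A second defence is that the line is damaged: it has lost its item number and may have lost a qualifier such as *more than* or *outside*. The missing number is only formatting. The sentence itself is complete and legible, and it is the rule that staff would apply. If it was meant to say the opposite, that is a reason to correct it.

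A third is that Procedure (b), by requiring day 30 from everyone, already shuts out late arrivals. That has some force, but no listed criterion says so, and screening works from the list.

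Two cautions stand. The plan does not name day 30 as the reference visit or tie the Friedman test to the three visits. Both are inferences from three related samples per person. And the documents cannot settle what the line was meant to say.

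**Conclusion.** The concern holds. Read literally, the second exclusion criterion bars people at the first required visit and bars no one who is already past it, and nothing elsewhere in the plan repairs this. The conflict touches day 30 directly; the day-60 and day-120 samples are not themselves inside the excluded window.

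Up to 80 of 240 planned samples are involved: all 80 if eligibility is judged at the first draw, none if everyone is assessed before day 25. The effect on the repeated-measures comparison assumes that the Friedman test will be run across the three visits. The contradiction in the text does not depend on that assumption. Because this is an operative eligibility rule, it must be corrected.

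**What to change.** Reconcile the Inclusion criteria, the Exclusion criteria and Procedure (b). The sponsor should first confirm what the 30 +/- 5 day line was meant to do. If it was meant as the window for the first sample, either of these would work:

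- reword the exclusion so that it removes people whose first blood sample cannot be taken within 30 +/- 5 days of completing the vaccination schedule; or
- delete it from the exclusions and add an inclusion criterion that the first sample is taken within 30 +/- 5 days of completion.

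Either form admits people who can give the day-30 sample and screens out those who have missed it. Add a short statement of when eligibility is assessed relative to completion of the schedule, and give Procedure (b) the same tolerance for the first visit so that the sections agree.

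The cost is about one line of protocol wording, plus the clarification of timing. No extra participants or procedures are needed.
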